7.18.2. Statistical Methods for PD Parameters

Plasma PD parameters will be summarized by treatment group using descriptive statistics (number of non-missing observations, arithmetic mean, SD, median, minimum, maximum,

CONFIDENTIAL

geometric mean, and geometric CV%). For the calculation of summary statistics, all NR and not calculated (NC) values in a data series will be set to missing.

Analyses of AUC for both $7\alpha C4$ and FGF19, C_{max} for FGF19, and C_{min} for $7\alpha C4$ at Day 1 and Week 12 will be carried out using an analysis of variance (ANOVA) model with the PD parameter as the dependent variable including treatment group as a fixed effect. The estimate of the LS means, SE, and 95% CIs will be presented by treatment group. Estimates of the LS mean difference for each pairwise comparison will be presented with associated the standard error of the difference, and 95% CI of the difference.

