Trough PD Sampling ^c		X	х	Х	х		х		Х	Refer to Appendix 2 for additional detail.
NASH/ Fibrosis Biomarkers ^c		х			х		х		х	Includes CK-18 (M30 and M65), ELF (PIIINP, TIMP-1, HA), and PRO-C3.
Intensive PK Sampling (PK/PD sub-study only)		х					Xi			Intensive PK sampling will be performed pre-dose and 1, 2, 4, 6, and 24 hours post the first dose of study drug on Week 0/Day 1, and at pre-dose and 1, 2, 4, 6, 24, 48, and 72 hours post last dose of study drug at Week 12. Patients should be instructed to hold their dose of study drug until after pre- dose and after 24-hour PK samples are collected. Refer to Appendix 2 for additional detail.
Intensive PD Sampling (PK/PD sub-study Only)		х					Xj			7α C4 and FGF19 will be collected at matching timepoints to Intensive PK sampling (above) except at Week 12 when 7α C4 and FGF19 will not be collected at 48 and 72 hours post dose. Refer to Appendix 2 for additional detail.
Clinical Laborator	y Procedure	es/Assessn	nents							
Patient Fasting	х	х	х	х	х	х	х	х	х	Patients must be in fasted state for at least 8 hours prior to blood collection and treatment administration, where applicable.

	Screening]	Freatmen	t Period ^f			Follow -Up ^b ET ^a		Notes	
Visit	Screening	Week 0	Week 2	Week 4	Week 6	Week 8	Week 12	Week 16			
Study Day		Day 1	15	29	43	57	85	113			
Schedule Window (days)	-42 days		± 3	± 3	± 3	± 3	± 3	-7 /+2		Patients discontinuing the study at any time for any reason (Early Termination) should complete the ET visit as soon as feasible and return for a Follow-Up visit 4 weeks (-7 days /+2 days) after the last dose of study drug.	
Chemistry ^e	x	x	x	x	x	x	x	x	X	Specific analytes are listed in Appendix 1. ALT and AST stability may be evaluated prior to randomization per Section 5. Increased monitoring criteria for elevated ALT and/or AST above 2×Baseline or above 5×ULN, and elevated ALP above 3×ULN are outlined in Appendix 3. A standard lipid test will be collected as part of the clinical chemistry at Screening to confirm eligibility (Appendix 1). During study treatment, lipid parameters for PD assessments listed in Table 9 of Appendix 2 will be collected and results will be blinded. HDL will remain unblinded and will be collected as part of clinical chemistry at all visits. Refer to Appendix 5 for the eGFR formula, to be calculated by central lab.	
Hematology ^c	х	Х	х	Х	Х	Х	Х	Х	x	Specific analytes are listed in Appendix 1.	

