9.4.4.3. Pharmacodynamic Endpoints

PD markers of THR- β agonism include SHBG and lipids, while PD markers of FXR agonism include FGF19, 7 α C4, and bile acids. Descriptive statistics of PD marker results, change from baseline, and percent change from baseline will be summarized by treatment group and visit. Change (and separately percent change) from baseline will be analyzed at applicable time points using the same ANCOVA model specified for the primary endpoint.

Pharmacodynamic parameters may also be calculated, summarized, and described by plotting the concentration-time curve or time-effect curve.

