Appendix 2: Sample Collection for Pharmacokinetics and Pharmacodynamics

Table 8 presents a description of PK/PD sample requirements at each study visit and timepoint.

Week	Day	Timepoint	Sample Type
0	1	Pre-dose (All Patients)	 Patients in PK/PD sub-study TERN-501, TERN-101, and TERN-101 metabolite TRN-000971 PK samples (PK/PD sub-study) Lipid Panel, 7αC4, FGF19, bile acids, and SHBG PD samples (PK/PD sub- study) Patients not participating in PK/PD sub- study Lipid Panel, 7αC4, bile acids, and SHBG PD samples
		 Post dose at the following timepoints (PK/PD sub-study only): 1 hour ± 5 minutes 2 hour ± 15 minutes 4 hours ± 15 minutes 6 hours ± 15 minutes 24 hours ± 1 hour prior to dosing on Day 2 	 TERN-501, TERN-101, and TERN-101 metabolite TRN-000971 PK samples 7αC4 and FGF19 PD samples
2	15 ± 3	Pre-dose (All Patients)	 TERN-501, TERN-101, and TERN-101 metabolite TRN-000971 PK samples Lipid Panel, 7αC4, and SHBG PD samples
4	29 ± 3	 Pre-dose (All Patients – PD samples) One sample between 2 and 6 hours post dose (All Patients – PK samples) 	 Lipid Panel, 7αC4, and SHBG PD samples TERN-501, TERN-101, and TERN-101 metabolite TRN-000971 PK samples
6	43 ± 3	Pre-dose (All Patients)	 TERN-501, TERN-101, and TERN-101 metabolite TRN-000971 PK samples Lipid Panel, 7αC4, and SHBG PD samples
8	57 ± 3	Pre-dose (All Patients)	TERN-501, TERN-101, and TERN-101 metabolite TRN-000971 PK samples
12	85±3	Pre-dose (All Patients)	 Patients in PK/PD sub-study TERN-501, TERN-101, and TERN-101 metabolite TRN-000971 PK samples Lipid Panel, 7αC4, FGF19, bile acids, and SHBG PD samples

Table 8PK/PD Sampling Timepoints

			 Patients not participating in PK/PD substudy TERN-501, TERN-101, and TERN-101 metabolite TRN-000971 PK samples Lipid Panel, 7αC4, bile acids, and SHBG PD samples
		 Post dose at the following timepoints (PK/PD sub-study only): 1 hour ± 5 minutes 2 hour ± 15 minutes 4 hours ± 15 minutes 6 hours ± 15 minutes 24 hours ± 1 hour on Day 86 PK only: 48 hours ± 2 hours on Day 87 72 hours ± 4 hours on Day 88 	 TERN-501, TERN-101, and TERN-101 metabolite TRN-000971 PK samples 7αC4 and FGF19 PD samples (up to 24 hours ± 1 hour on Day 86 only)
ET	ET	• At the ET Visit, for all patients discontinuing the study at any time for any reason (Early Termination)	 TERN-501, TERN-101, and TERN-101 metabolite TRN-000971 PK samples Lipid Panel, 7αC4, FGF19, bile acids, and SHBG PD samples

PD Sample Collection

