2.1. Overall Study Design

This study is a multicenter, randomized, double-blind, placebo-controlled, parallel-group treatment, phase 2a study.

Approximately 140 non-cirrhotic NASH patients with fibrosis identified based on prior liver biopsy and/or imaging and clinical criteria who meet study eligibility criteria will be enrolled and randomized equally into 7 groups: once daily orally administered TERN-501 1 mg (n=20), TERN-501 3 mg (n=20), TERN-501 6 mg (n=20), TERN-501 10 mg (n=20), TERN-101 10 mg (n=20), or matching placebo (n=20).

Of the 140 patients randomized, approximately 42 patients (approximately 6 per group) will take part in an intensive PK and pharmacodynamic (PD) collection after the first dose and after the last dose of study drug. Patients who are not participating in the PK/PD sub-study will have sparse PK and trough PD sampling only.

The total study duration will be approximately 22 weeks, consisting of a 6-week Screening Period, a 12-week Treatment Period, and a 4-week Follow-up Period.

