7.1. Adjustments for Covariates

The Baseline value will be used as a covariate in each ANCOVA model.

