7.18. Pharmacodynamic Analyses

The pharmacodynamic (PD) endpoints of SHBG, lipid panel, FGF19, 7α C4, and bile acids are collected at the timepoints shown in Table 8 of the protocol.

The change from baseline in SHBG, LDL-c, will be analyzed in the same manner as specified in Section 7.7 and pairwise comparisons in Section 7.6 using the efficacy analysis set.

Plasma concentrations for $7\alpha C4$, FGF19, and bile acids that are BLQ will be set to $\frac{1}{2} \times BLQ$. Plasma PD parameters will be computed for PD patients only. Plasma PD parameters for $7\alpha C4$ and FGF19 will be calculated from the individual plasma concentrations using a non-compartmental approach for Day 1 and Week 12. Day 1 will include pre dose and all post dose assessments prior to dosing on Day 2. Week 12 will include pre dose and all post dose assessments. The actual PD sampling times will be used for the PD analysis. If actual PD sampling times are missing, nominal times will be used. Table 1 below presents the plasma PD parameters to be calculated.

Final, Version 2.0, 26JULY2023

CONFIDENTIAL

Labcorp Drug Development Study: 000000231152 Protocol Reference: TERNCB-2002

Table 10 Plasma PD Parameters

Abbreviation	Parameter Definition
AUEC ₀₋₂₄	Area under the effect-time curve from time 0 to 24 hours postdose
RAUEC	Ratio of AUEC (Week 12) /AUEC (Day 1).
C_{\min}	For $7\alpha C4$ only, minimum observed plasma concentration, obtained directly from the plasma concentration-time profiles. In the case where multiple minimums are of equal magnitude, the earliest minimum concentration will be reported as C_{min} .
RC _{min}	For $7\alpha C4$ only, ratio of $C_{min (Week 12)}/C_{min (Day 1)}$.
C _{max}	For FGF19 only, maximum observed plasma concentration, obtained directly from the plasma concentration-time profiles. In the case where multiple peaks are of equal magnitude, the earliest peak concentration will be reported as C_{max} .
RC _{max}	For FGF19 only, the ratio of $C_{max (Week 12)} / C_{max (Day 1)}$.
t _{min}	For $7\alpha C4$ only, time of the minimum observed plasma concentration, obtained directly from the plasma concentration-time profiles. In the case where multiple minimums are of equal magnitude, the time of the earliest minimum will be reported as the t_{min} .

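### The 7αC4 and FGF19 profile parameters are compared by an ANOVA that leaves out the Day 1 pre-dose value, so with about 6 patients per arm this exploratory comparison is probably less precise than it could be

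*SAP*

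**What the plan says.** SAP 7.18.2 covers AUC for 7αC4 and FGF19, Cmax for FGF19 and Cmin for 7αC4, each on two occasions, Day 1 and Week 12. It describes these analyses as "carried out using an analysis of variance (ANOVA) model with the PD parameter as the dependent variable including treatment group as a fixed effect". It reports LS means, SEs and 95% CIs by arm and for each pairwise difference. It names no covariate and no p-value.

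The SAP's covariate rule in 7.1 reads "The Baseline value will be used as a covariate in each ANCOVA model". It applies to ANCOVA models, so it does not reach this ANOVA.

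The baseline is available. Protocol Appendix 2, Table 8 lists "Lipid Panel, 7αC4, FGF19, bile acids, and SHBG PD samples" at Week 0 pre-dose for sub-study patients. The Schedule of Activities sets the Day 1 PK times ("Intensive PK sampling will be performed pre-dose and 1, 2, 4, 6, and 24 hours post the first dose of study drug") and has 7αC4 and FGF19 collected at matching times.

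Protocol 9.4.4.3 names FGF19 and 7αC4 as PD markers and plans change from baseline "using the same ANCOVA model specified for the primary endpoint", which includes baseline as a covariate. SAP 7.18 assigns the Section 7.7 ANCOVA only to SHBG and LDL-c. SAP Section 10 reports no changes from the protocol's planned analyses.

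On size, SAP 2.1 says "approximately 42 patients (approximately 6 per group) will take part in an intensive PK and pharmacodynamic (PD) collection".

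**The concern.** 7αC4 and FGF19 are endogenous, so each patient's profile starts from a personal level. If that level predicts the profile parameter, an analysis without it leaves explainable between-patient variation in the error term. A chance difference in starting level between two arms of 6 then moves the estimated arm difference.

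These parameters are meant to show FXR engagement with TERN-101 alone and in combination. The sponsor has used 7αC4 this way before: protocol 4.3 cites its apparent plateau when justifying the TERN-101 dose. FGF19 is not drawn at scheduled visits outside the sub-study, so the 7.18.2 ANOVA is the only between-arm FGF19 model that the SAP spells out.

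The Week 12 to Day 1 ratios in SAP Table 10 (RAUEC, RCmin, RCmax) do not supply the missing adjustment. Their denominator is the Day 1 profile, which is mostly post-dose, and they are not among the variables listed for the ANOVA.

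**Working it through.** The documents state no power or precision for the sub-study, so there is no sub-study figure to reproduce. The nearest stated figure is the primary power in SAP 2.3 (difference 23%, SD 22%, 20 per arm, two-sided 0.05, about 90%). A two-sample t test gives 89.6%, so it reproduces, but it does not bear on this point.

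**Inputs.** 7 arms of about 6 (SAP 2.1), so 42 patients. Residual df: 42 − 7 = 35 for the ANOVA, 34 with one covariate. Two-sided 95% CIs. The within-arm correlation ρ between the pre-dose value and the profile parameter is an assumption, shown as a range. Widths are in between-patient SDs on whatever scale is analysed.

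**ANOVA half-width** for one arm difference: t(0.975, 35) × √(2/6) = 2.030 × 0.577 = 1.17 SD.

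**ANCOVA half-width:** t(0.975, 34) × √[(2/6)(1 − ρ²)(1 + 1/33)], with t = 2.032. The factor 1 + 1/33 is the average cost of estimating the slope (33 = 35 − 2).

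| Assumed ρ | Half-width (SD) | Relative to ANOVA |
|---|---|---|
| 0 | 1.19 | 1.6% wider |
| 0.2 | 1.17 | 0.4% narrower |
| 0.3 | 1.14 | 3% narrower |
| 0.5 | 1.03 | 12% narrower |
| 0.7 | 0.85 | 27% narrower |
| 0.8 | 0.71 | 39% narrower |

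A simulation with 8,000 replicates, run at ρ = 0, 0.2, 0.5 and 0.7, gave the same relative widths to within 0.1 percentage point.

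**Break-even.** The two widths are equal when (1 − ρ²)(34/33)(2.0322/2.0301)² = 1, that is ρ ≈ 0.18. With only 4 evaluable patients per arm, break-even is about 0.24 and the penalty at ρ = 0 is about 3%.

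**Equivalent sample size.** Solving t(0.975, 7n − 7) × √(2/n) for the ANCOVA half-widths at ρ = 0.5, 0.7 and 0.8 gives n of about 7.6, 11 and 15 per arm under ANOVA. The shortcut 6/(1 − ρ²) gives 8, 12 and 17, which overstates the gain because it ignores the cost of the slope.

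**Chance imbalance.** The difference in mean baseline between two arms of 6 has SD √(2/6) = 0.577 baseline SD. It exceeds 0.5 SD in 39% of pairs and 1 SD in 8%. An imbalance shifts the ANOVA estimate by ρ times its size: 0.5 SD at ρ = 0.5 gives 0.25 SD, about one fifth of the 1.17 SD half-width. Over all replicates the simulated ANOVA coverage stayed at about 95%. Among replicates with an imbalance above 1 SD it was about 84% at ρ = 0.5 and 73% at ρ = 0.7.

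**The case against.** The strongest reply is that little depends on this analysis. The markers are exploratory, 7.18.2 specifies no p-value, and protocol 9.4.4.3 says only that PD parameters may be calculated and described, so the ANOVA already goes beyond the protocol. Trough 7αC4 is sampled in all patients at several visits, so the sub-study is not the only evidence of FXR engagement. All of this stands and limits the weight of the point.

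It is also fair that the gain depends on an undocumented correlation, which could be low. The covariate is one fasting sample, while the profile spans 24 hours with food allowed from 2 hours post-dose (protocol 5.3.2). That is why the table starts at zero. The trade remains lopsided: about 2% to lose at ρ = 0, and 12% to 39% to gain at ρ from 0.5 to 0.8.

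A reader might infer that the ANOVA is biased, or that imbalance passes in full into the arm comparison. Neither follows. Randomisation keeps the estimate unbiased on average, the interval already allows for chance baseline variation, and only ρ times an imbalance is carried over.

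A reader might also infer that the SAP offers the Week 12 to Day 1 ratios as effect against the untreated state. It defines them without giving them that role.

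Finally, dividing the parameters by the pre-dose value is tempting but unsound on Day 1. SAP 7.18 states "Day 1 will include pre dose and all post dose assessments prior to dosing on Day 2". Cmin over pre-dose therefore cannot exceed 1 and Cmax over pre-dose cannot fall below 1, on placebo too. Scaling AUEC by 24 times the pre-dose value assumes a flat untreated profile, and no untreated 24-hour profile is collected.

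**Conclusion.** The point holds as a question of efficiency and of protection against chance imbalance in an exploratory sub-study. SAP 7.18.2 omits a baseline that is already collected and that protocol 9.4.4.3 would use for these markers. Adjustment narrows the interval if the within-arm correlation exceeds about 0.18, by an amount that the documents do not allow anyone to fix. The figures assume 6 evaluable patients in each of 7 arms, a common variance and a linear relation on the analysed scale.

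The case is cleanest at Week 12. On Day 1 the pre-dose sample is one point of the profile and may itself be the Cmin or Cmax, so it is not wholly unused there. The documents do not support a finding of systematic bias. The primary and secondary endpoints and the sample size are unaffected. The change is worth making because it is nearly free.

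**What to change.** In SAP 7.18.2, replace the ANOVA with an ANCOVA containing treatment group and the patient's Day 1 pre-dose concentration of the same marker. Put outcome and covariate on the log scale. SAP 3.5 already permits a transformation, and 7.18.2 already reports geometric means and geometric CVs for these parameters, but the scale should be fixed in advance.

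Apply the model chiefly to the Week 12 parameters. If it is also used on Day 1, state that the covariate is part of the profile and interpret the result with care. Do not add Day 1 Cmin/pre-dose or Cmax/pre-dose ratios as effect measures. If the ANOVA is kept, record in SAP Section 10 how the handling of 7αC4 and FGF19 departs from protocol 9.4.4.3.

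The cost is a wording change and one model term, with no new samples. It uses 1 of about 35 residual degrees of freedom, and the interval is about 2% wider if the correlation is zero.

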7.18.3. PK/PD Analyses

For patients in the PK/PD substudy, Day 1 and Week 12 PK and PD (7α C4 and FGF19) concentrations will be plotted together by treatment group over time. Similarly, AUCs, C_{min} , and C_{max} for PK and PD will also be plotted by treatment group.

Final, Version 2.0, 26JULY2023

CONFIDENTIAL

8. Safety Analyses

All safety analyses will be conducted using the safety analysis set unless otherwise noted.

8.1. Extent of Exposure

Total duration of exposure will be calculated in days as the last date study drug administration – the first date study drug administration + 1. In addition, duration of exposure accounting for days where a dose was missed (referred to as interruptions on CRFs) will be calculated as total duration – sum of (Week X date of resumption – Week X start date of interruption) where X is the week number, i.e., 2, 4, 6, 8, and 12. The dates of interruption are from the Study Drug Interruptions CRF. If dates of missed doses are not available, the number of missed doses will be used. Duration of exposure, total and accounting for missed dosing days, will be summarized with descriptive statistics by treatment group.

The number and percentage of patients with any missed dose and the total duration of days where doses were missed will be summarized with descriptive statistics by treatment group.

Compliance based on the Study Drug Administration and Study Drug Interruptions CRFs will be calculated as:

• 100 × [((last date study drug administration – the first date study drug administration + 1) – sum of durations interrupted) / (last date study drug administration – the first date study drug administration + 1)].

Compliance will be calculated based on the Study Drug Accountability CRF as:

• $100 \times [(Sum \text{ of tablets or capsules taken during study}) / (Expected Taken)]$

Tablets and/or Capsules will be summed across all bottles, whether monotherapy or combination, at each week.

Expected taken is calculated as the study day of the last dose date × 4 (number of tablets or capsule taken per day). Treatment compliance will be summarized with descriptive statistics by treatment group. The number and percentage of patients in each of the following compliance categories will be summarized by treatment group and overall total:

Final, Version 2.0, 26JULY2023

CONFIDENTIAL

- < 80%
- 80% to $\leq 100\%$
- > 100%.

Study drug administration including missed doses, delays, and overdoses, and study drug dispensing and accountability, calculated durations of exposure, and calculated compliance will be presented in by-patient data listings.

8.2. Adverse Events

Adverse event (AE) verbatim terms on eCRFs will be mapped to preferred terms (PT) and system organ classes (SOC) using MedDRA. AE severity will be categorized using the National Cancer Institute Common Terminology Criteria for Adverse Events (NCI CTCAE, Version 5).

[figure not shown]
All AEs will be listed, but summaries will be restricted to treatment emergent AEs (TEAEs), defined as any AE with a start date on or after the date of first administration of study drug through 30 days after the last administration of study drug or through the Follow-Up Period (Week 16). Related SAEs after Week 16 will be considered TEAEs. If it cannot be determined whether an AE is treatment emergent due to a partial onset date, then it will be counted as such. Methodology for imputation of partial AE start and stop dates is described in Appendix 2. Each summary will be displayed by treatment group.

8.2.1. Overall Summary of Adverse Events

An overall summary of TEAEs will be presented by treatment group. The number and percentage of patients who experience at least one of the following:

- Any TEAE, All CTCAE grades
- Grade 3 or higher TEAE
- Serious TEAE
- TEAE leading to death
- Treatment-related TEAE, All CTCAE grades
- Treatment-related Grade 3 or higher TEAE
- Treatment-related serious TEAE
- TEAE leading to study drug interruption
- TEAE leading to study drug discontinuation
- TEAE leading to discontinuation from the study

CONFIDENTIAL

8.2.2. Patient Incidence of Adverse Events

6.2.2. I dient incluence of Adverse Events

Summaries will be displayed by SOC and PT and will be ordered by descending order of group 7 incidence of system organ class and preferred term within each system organ class. Summaries of the following types will be presented:

- Patient incidence of TEAEs by MedDRA SOC and PT.
- Patient incidence of TEAEs leading to study drug discontinuation by MedDRA SOC and PT. This is a subset of the AEs where Action Taken with Study Drug is checked as "Drug Withdrawn."
- Patient incidence of TEAEs leading to study drug interruption by MedDRA SOC and PT. This is a subset of the AEs where Action Taken with Study Drug is checked as "Drug Interrupted."
- Patient incidence of TEAEs leading to study discontinuation by MedDRA SOC and PT (subset of the AEs where Reason for Discontinuation on the End of Study CRF is "Adverse Event").
- Patient incidence of TEAE leading to death by MedDRA SOC and PT.
- Patient incidence of TEAEs by MedDRA SOC, PT, and highest severity (CTCAE grade). At each level of patient summarization, a patient is classified according to the highest severity if the patient reported 1 or more events. AEs with missing severity (CTCAE grade) will be considered Grade 3 (severe) for this summary.
- Patient incidence of CTCAE Grade 3 or higher TEAEs by MedDRA SOC and PT. At each level of patient summarization, a patient is classified according to the highest severity if the patient reported 1 or more events. AEs with missing severity (CTCAE grade) will be considered Grade 3 (severe) for this summary.
- Patient incidence of treatment-related TEAEs by MedDRA SOC and PT. Related AEs
 are those with relationships reported as "Related" or "Possibly Related". At each level
 of patient summarization, a patient is classified according to the closest relationship to
 study drug if the patient reported 1 or more events. AEs with a missing relationship
 will be considered related for this summary.
- Patient incidence of treatment-related CTCAE Grade 3 or higher TEAEs by MedDRA SOC and PT. At each level of patient summarization, a patient is classified according

CONFIDENTIAL

to the highest severity if the patient reported 1 or more events. AEs with missing severity (CTCAE grade) will be considered Grade 3 (severe) for this summary. AEs with a missing relationship will be considered related for this summary.

• Patient incidence of serious TEAEs by MedDRA SOC and PT.

The following listings will be presented by treatment group and patient, include study day event started and the duration of event:

- All adverse events.
- Serious adverse events (subset of the AEs where serious is marked as "Yes").
- Adverse events leading to study drug interruption (subset of the AEs where Action Taken with Study Drug is checked as "Study drug interrupted").
- Adverse events leading to study drug discontinuation (subset of the AEs where Action Taken with Study Drug is checked as "Study drug discontinued").
- Adverse events leading to study discontinuation (subset of the AEs where Reason for Discontinuation on the End of Study CRF is "Adverse Event").
- CTCAE Grade 3 or higher adverse events (subset of AEs where severity is marked as CTCAE Grade 3, 4, or 5).
- Related adverse events (subset of the AEs where relationship marked as "Definitely Related" or "Possibly Related").
- CTCAE Grade 3 or higher treatment-related adverse events (subset of AEs where severity is marked as CTCAE Grade 3, 4, or 5).

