10.1.7. Source Documents

Source documents provide evidence for the existence of the patient and substantiate the integrity of the data collected. Source documents are stored at the Investigator's site.

Data reported on the eCRF or entered in the eCRF that are transcribed from source documents must be consistent with the source documents or the discrepancies must be explained. The Investigator may need to request previous medical records or transfer records, depending on the study.

The required source data should include notes containing at least the following information for each patient:

- Patient identification (name, date of birth, gender)
- Documentation that the patient meets eligibility criteria
- Documentation of the reason(s) a consented patient is not enrolled
- Participation in study (including study number)
- Study discussed and date of informed consent
- Dates of all visits
- Documentation that protocol-specific procedures were performed
- Start and end date (including dose regimen) of study drug administration, including dates of dispensation and return as applicable
- Record of all AEs and other safety parameters (start and end date, and including causality and severity)
- Concomitant medications (including start and end date, dose if relevant; dose changes)
- Date of study completion and reason for early discontinuation, if applicable

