6.1. Patient Disposition

Patient disposition will be summarized for the Screening Analysis Set by treatment group and overall total. The summary will include:

- Number of patients screened.
- Number of screen failures, i.e., screened but not randomized, with reasons for screen failure. The denominator for percentage of screen failures will be the number of patients screened. The denominator for percentages for reasons for screen failures will be the number of screen failures.
- Number randomized. The denominator for percentage of randomized patients will be the number of patients screened.
- Number randomized and not treated. The denominator for percentage of randomized and not treated patients will be the number of patients randomized.
- Number in each analysis set. The denominator for percentage in each analysis set will be the number of randomized patients. In addition, the number of patients randomized to the PK/PD substudy will be presented.
- Number who discontinued treatment early and reason(s) for discontinuation of treatment. The denominator for percentages will be the number of randomized and treated patients (Efficacy Analysis Set).
- Number who discontinued from study prior to completing the study and reason(s) for discontinuation. The denominator for percentages will be the number of randomized and treated patients (Efficacy Analysis Set).

A by-patient data listing of study disposition information including the reasons for treatment and/or study termination will be presented. Withdrawal of consent details will also be included, if applicable.

A by-patient data listing including the reasons for exclusion from each analysis set will be presented.

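### SAP 8.2.2 selects adverse events leading to study discontinuation by a patient-level exit reason and does not say how the causative event is identified

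*SAP*

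**What the plan says.** Among the SOC/PT tables in SAP 8.2.2 is one for TEAEs that ended study participation, defined by the words "study discontinuation by MedDRA SOC and PT (subset of the AEs where Reason for Discontinuation on the End of Study CRF is", with the value Adverse Event. Further down the section a by-patient listing uses the same condition: "Adverse events leading to study discontinuation (subset of the AEs where Reason for Discontinuation on the End of Study CRF is", again with the value Adverse Event.

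Two neighbouring tables are built differently. One is "Patient incidence of TEAEs leading to study drug discontinuation by MedDRA SOC and PT. This is a subset of the AEs where Action Taken", where the recorded action is withdrawal of the drug. The other is "Patient incidence of TEAEs leading to study drug interruption by MedDRA SOC and PT. This is a subset of the AEs where Action Taken", where it is interruption. Both rest on a field of the individual event.

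Elsewhere the reason for leaving appears as information about the patient. The disposition summary in SAP 6.1 reports "Number who discontinued from study prior to completing the study and reason(s) for discontinuation". Protocol 10.1.7 asks for the following in each patient's source notes: "Date of study completion and reason for early discontinuation, if applicable". The overall summary in SAP 8.2.1 counts patients with at least one "TEAE leading to discontinuation from the study".

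**The concern.** The title of the table promises the events that caused patients to leave. The condition that follows it identifies the patients who left for an adverse event, which is a different thing. A patient-level condition cannot separate the causative event from the patient's other events. A programmer who applies the rule literally will therefore enter unrelated preferred terms as reasons for exit, and a second programmer validating from the same text will reproduce the error.

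What is at stake is attribution. The table and listing would credit some study exits to events that had nothing to do with them. The drug-discontinuation table does not fill the gap, because the protocol separates stopping drug from leaving the study. Under Protocol 7.1.2 a patient who permanently stops drug should stay for the remaining visits through Follow-Up.

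**Working it through.** No figure in the plan needs reproducing. The check sets the selection rules side by side and then shows the scale by hand arithmetic.

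**Step 1. Level of each selector.**

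| Output in SAP 8.2.2 | Field used | Level |
|---|---|---|
| TEAEs leading to drug discontinuation | Action taken with study drug | Event |
| TEAEs leading to drug interruption | Action taken with study drug | Event |
| Serious, Grade 3 or higher, and related events (listings) | Seriousness, severity, relationship | Event |
| Events leading to study discontinuation (table and listing) | End of Study reason | Patient |

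The last row is the only filter stated in these lists that relies on a form other than the adverse event record. That its level is the patient is inferred from SAP 6.1 and Protocol 10.1.7.

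**Step 2. Pool of events caught.** TEAEs run from first dose "through 30 days after the last administration of study drug or through the Follow-Up Period (Week 16"). Under Protocol 7.2, a patient who leaves early is asked back about 4 weeks after the last dose. The pool can therefore include events long before the exit and events that began after the decision to leave. The listing is titled for adverse events in general, so procedure-related events before dosing (Protocol 8.5.1) would also qualify there.

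**Step 3. Worked record (invented).** A patient has headache on Day 10, an upper respiratory infection on Day 25 and pruritus on Day 40, and leaves because of the pruritus. The End of Study reason is Adverse Event, so the condition is true for all three records. The literal rule gives three preferred-term entries where one is right, so 3 − 1 = 2 are false.

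**Step 4. Scale.** Inputs: 20 patients per arm (SAP 2.3). Assumed: m distinct preferred terms in the exiting patient, one of them the cause. The documents give no event count per patient.

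- False entries = m − 1; false share = (m − 1)/m.
- m = 1: 0 false.
- m = 2: 1 of 2 = 50%.
- m = 3: 2 of 3 = 67%.
- m = 4: 3 of 4 = 75%.
- Incidence shown per false entry = 1/20 = 5% in that arm's row.

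A SOC row is wrong only when an unrelated event falls in a different SOC from the cause. A repeat of the same preferred term leaves the PT row unchanged but still adds a false line to the listing.

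**Step 5. Overall count.** SAP 8.2.1 counts each patient once. The patient in Step 3 contributes 1 whether one or three events are selected, so that row does not move.

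**The case against.** The strongest reply is that the text should be read whole. Each bullet opens by limiting itself to events leading to study discontinuation, and the parenthesis may only say where the reason is recorded. The eCRF is a listed source for the SAP (Section 1), and output formats are left to separate shells (SAP 3.1). Neither is in the documents. If the End of Study page captures the number or term of the causative event, the parenthesis is shorthand for the linked event and the output would be right. That the form stands alone, once per patient, is an inference: SAP 6.1 describes a summary and Protocol 10.1.7 describes site notes, not the form's structure.

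This stands as a limit on certainty. A reader might infer that every TEAE of such a patient will certainly be reported as a cause of exit. The documents do not support that, because they do not show whether a link exists. The reply does not rescue the wording, however. The SAP names no link, and the condition it does state cannot deliver what the title promises.

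The second reply concerns weight, and it largely stands. Exits for adverse events should be few. The first-in-human TERN-501 study had no withdrawals due to adverse events (Protocol 2.2.1.2). In the 12-week TERN-101 study of 100 treated patients, none stopped TERN-101 or placebo for one (Protocol 2.2.2.2). These are other studies, so zero is not assured here. The listing also shows the study day of onset and the duration, and SAP 6.1 plans a disposition listing with reasons, so a careful reader could check the few cases by hand.

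**Conclusion.** The selection rule is wrong as written, and the correction is minor. Applied literally, it gives false PT entries, possibly false SOC entries, and false listing lines for any patient who left for an adverse event and also had TEAEs that were not the cause. Each false PT entry is worth 5% in an arm of 20. A patient with a single TEAE is classified correctly.

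This rests on two assumptions: that the End of Study page does not identify the causative event, and that programming follows the stated condition. The number of patients affected cannot be derived from the documents but is likely to be small.

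A reader might also infer that the trial's safety conclusions are distorted. The documents do not support this. The secondary safety endpoint is incidence of TEAEs (SAP 2.2.2.1), which does not use this filter. The drug-discontinuation table has its own event-level selector, the patient count in SAP 8.2.1 is unchanged, and no efficacy analysis or power figure is involved.

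**What to change.** In both places in SAP 8.2.2, the table bullet and the listing bullet, replace the parenthesis with an event-level selector: the adverse event(s) linked by event number to the End of Study record whose reason is Adverse Event.

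If the eCRF holds no such link, have the causative event(s) flagged in blinded review before database lock, and select on that flag.

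The cost is one sentence in two places and one derived flag in the adverse event analysis dataset. No new data are needed from patients. The downside, if there is no link, is a short review of the few patients concerned.
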